11.2.1. Best Overall Response

The best response recorded from the start of the treatment until disease progression/recurrence (taking as reference for progressive disease the smallest measurements recorded since the treatment started). The patient's best response assignment will depend on the achievement of both measurement and confirmation criteria.

11.2.2. Progression-Free Survival

The duration of time from start of treatment to time of progression or death, whichever occurs first. For those patients with a CR or PR, the reference for progressive disease the smallest measurements recorded since the treatment started).

11.2.3. Response Review

All responses will be reviewed by an expert radiologist and/or radiation oncologist at the study's completion, with simultaneous review of the patients' files and radiological images.

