13.2. Sample Size/Accrual Rate

The primary analysis will be for patients enrolled at time-points (A) and (B) above, whereas patients enrolled at time-point (C) will be included in observational analysis only (see section 3.1). The primary endpoint of this study is the overall response rate (complete + partial response) and the efficacy will be assessed using the Simon's two-stage Minmax design. A sample size of 33 patients is chosen to differentiate between the response rate of 20% and 40% with 80% power at a significance level of 0.05. In particular, 18 patients will be enrolled at the first stage. If 15 or more of the first 18 patients have disease progression prior to any response, the trial will be terminated; otherwise an additional 15 patients will be treated for a total of 33 patients. In the final data analysis, if 10 or fewer patients respond among 33 patients, the treatment will be concluded ineffective. The probability of early termination due to futility is 0.72.

For correlative study between biomarkers and response, this sample size will have at least 80% power to detect a 50% change/difference on biomarker data between response and non-response groups using a two-sided two-sample t-test at 0.05 significance level, assuming that the response rate is 35% or higher and the coefficient of variation (CV) of biomarkers is 0.45.

Approximately 100 patients with metastatic NSCLC are diagnosed and treated each year at our institution, many of whom will be candidates for immune checkpoint therapy. As such, we expect to accrue 3 patients per month to this trial for an estimated accrual period of one year. The full estimated duration of the study is two years.

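### The stage-1 futility decision comes before the plan's only expert review of responses, and the plan does not say which reads count at each stage

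*Combined protocol and SAP*

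**What the plan says.** Section 11.2.3 (Response Review) fixes the timing of the only expert check on the primary endpoint: "All responses will be reviewed by an expert radiologist and/or radiation oncologist at the study's completion". No other section provides for a review before that.

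Section 13.2 states that "the efficacy will be assessed using the Simon's two-stage Minmax design", with 33 patients chosen to "differentiate between the response rate of 20% and 40% with 80% power at a significance level of 0.05". It then says "18 patients will be enrolled at the first stage". The stopping rule is: "If 15 or more of the first 18 patients have disease progression prior to any response, the trial will be terminated". If that threshold is not reached, stage 2 brings in 15 more patients to make 33. At the end, "if 10 or fewer patients respond among 33 patients, the treatment will be concluded ineffective". It adds: "The probability of early termination due to futility is 0.72".

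Response has one definition for the whole trial: complete or partial response by irRC on non-irradiated lesions, with confirmation (synopsis, 11.1.2, 11.2, 11.2.1).

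Three things are not stated: whose reads feed the stage-1 decision, whether the end-of-study review can overturn an on-study read, and whether the final count of 33 uses on-study or reviewed reads.

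**The concern.** The stage-1 look is the trial's one formal adaptive decision, and on the stated timing it is made before the plan's quality check on the endpoint. The trial is non-randomized and everyone receives the combination (3.1), so on-study readers know the treatment.

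The reads are also demanding. They need bidimensional sums over up to 10 visceral lesions plus new lesions, exclusion of irradiated lesions, removal of an index lesion once it is irradiated, and confirmation at least 4 weeks later (11.1.2, 11.2). An on-study read can go wrong at any of these steps.

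If on-study reads are generous, a trial that reviewed data would have stopped goes on to treat 15 more patients. If they are strict, a useful treatment may be dropped at 18 patients, and no later review can recover it.

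**Working it through.** **Inputs from 13.2.** Stage 1 n1 = 18, total N = 33, null rate 0.20, target rate 0.40, power 80%, alpha 0.05, ineffective if 10 or fewer of 33 respond, early termination 0.72.

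**Step 1: reproduce the plan.** An exact search for the minimax design returns: stop if 4 or fewer of 18 respond; declare ineffective if 10 or fewer of 33 respond. Early termination at 0.20 is P(Bin(18, 0.20) ≤ 4) = 0.0180 + 0.0811 + 0.1723 + 0.2297 + 0.2153 = 0.716, the stated 0.72. Type I error is 0.0458 and power 0.8011. Expected sample size at 0.20 is 18 + 15 × (1 − 0.7164) = 22.25.

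This 4/18 boundary is used below because it is the one that gives 0.72. The rule as written (15 or more of 18 progressing first) would, if every non-responder had progressed, mean stopping at 3 or fewer responders. Its early-termination probability is 0.501, so it does not match 0.72. That is a separate defect.

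**Step 2: allow the on-study read to differ from the review.** Let p be the reviewed response rate, s the share of reviewed responders that the on-study read also calls responders, and f the share of reviewed non-responders that it calls responders. The on-study response rate is q = p·s + (1 − p)·f, and the stage-1 stop probability is P(Bin(18, q) ≤ 4). The documents give no s or f. Assumed ranges: s from 0.80 to 1.00, f from 0 to 0.10.

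**Step 3: final count on reviewed reads of all 33.** The probability of declaring success is the sum over x of P(Bin(18, p) = x) × P(on-study count ≥ 5 given x reviewed responders) × P(Bin(15, p) ≥ 11 − x).

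| s | f | q at p = 0.20 | Early stop at 0.20 | Type I error | q at p = 0.40 | False stop at 0.40 | Power |
|---|---|---|---|---|---|---|---|
| 1.00 | 0 | 0.20 | 0.716 | 0.046 | 0.40 | 0.094 | 0.801 |
| 1.00 | 0.05 | 0.24 | 0.559 | 0.048 | 0.43 | 0.058 | 0.814 |
| 1.00 | 0.10 | 0.28 | 0.403 | 0.049 | 0.46 | 0.034 | 0.822 |
| 0.90 | 0 | 0.18 | 0.788 | 0.040 | 0.36 | 0.166 | 0.753 |
| 0.90 | 0.05 | 0.22 | 0.639 | 0.044 | 0.39 | 0.109 | 0.783 |
| 0.90 | 0.10 | 0.26 | 0.479 | 0.047 | 0.42 | 0.069 | 0.802 |
| 0.80 | 0 | 0.16 | 0.852 | 0.033 | 0.32 | 0.269 | 0.673 |
| 0.80 | 0.10 | 0.24 | 0.559 | 0.043 | 0.38 | 0.126 | 0.762 |

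The ceiling with no binding interim stop is P(Bin(33, 0.20) ≥ 11) = 0.0508 for type I error and 0.831 for power.

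**Step 4: expected sample size at 0.20.** It is 18 + 15 × (1 − 0.4032) = 26.95 at the generous end and 18 + 15 × (1 − 0.8518) = 20.22 at the strict end, against 22.25.

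**Step 5: the other branch, on-study reads in both counts.** The stages then match. However, at a reviewed rate of 0.20, over-calling by f = 0.05 or 0.10 (q = 0.24 or 0.28) gives a success probability of 0.134 or 0.282. That follows from read accuracy, not from the timing of the review, but it is why the plan should say which reads count.

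**The case against.** A reader might infer that the two Simon stages use different endpoints. The documents do not support that. Response has one definition, and nothing says that reviewed reads replace on-study reads. If on-study reads count throughout, the stages agree. If reviewed reads count at the end, the final rule covers all 33 patients, so both cohorts are judged alike and only the futility look could differ. The stage-1 rule is indeed worded in progressions while the final rule counts responses, but that does not come from the review timing.

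A reader might also infer an inflated type I error. With reviewed reads at the end there is none of note (0.033 to 0.049; ceiling 0.0508), and pure over-calling slightly raises power.

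A third inference is that only called responders are reviewed, so that review could only remove responders. This is not the natural reading: 11.1.2 and 11.2 use the word response for every category, including stable and progressive disease.

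It can further be said that on-study reads are not loose, since measurement is to the nearest millimetre (11.1.1) and confirmation is required. A decision to continue is also not final, because 3.6 allows termination at any time. Both are fair. They limit the likely size of the effect, but they do not put reviewed reads in front of the stage-1 decision or say which reads it uses.

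**Conclusion.** The point holds as a gap in timing and specification. As written, the stop/go decision on the first 18 patients uses reads that have not had the only planned expert review, and the classification behind each count is not stated.

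If the final count uses reviewed reads, type I error is protected and the effect is confined to the futility look. Early termination at a true 20% ranges from about 0.40 to 0.85 against 0.72, and power from about 0.67 to 0.82 against 0.80. Generous reads cost up to about 5 more expected patients (26.95 − 22.25 = 4.70). Strict reads cost power.

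These ranges rest on assumed misread rates and on the 4/18 boundary implied by 0.72, not on the rule as worded. If on-study and reviewed reads agree fully, the design performs as stated. The change is worth making because it is cheap and the stage-1 decision may be final.

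**What to change.** Amend 11.2.3 so that the expert review already planned is done in two batches: the response classification of the first 18 patients, in all categories, before the stage-1 decision; and that of the remaining patients before the final analysis, together with any later scans of the first 18. State in 13.2 that the stage-1 count and the final count both use the reviewed classification.

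The cost is a short delay at stage 1 and a review split in two. No reviewer is added. The mismatch between the written stage-1 rule and the stated 0.72 should be reconciled in the same amendment, since the reviewed count needs a clear boundary.

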12. DATA REPORTING / REGULATORY CONSIDERATIONS

Adverse event lists, guidelines, and instructions for AE reporting can be found in Section 7.0 (Adverse Events: List and Reporting Requirements).

12.1. Data Reporting

The OnCore Database will be utilized, as required by the WVU MBRCC, to provide data collection for both accrual entry and trial data management. OnCore is a Clinical Trials Management System housed on secure servers maintained at West Virginia University. OnCore properly used is compliant with Title 21 CFR Part 11. Access to data through OnCore is restricted by user accounts and assigned roles. Once logged into the OnCore system with a user ID and password, OnCore defines roles for each user which limits access to appropriate data. User information and password can be obtained by contacting the OnCore Administrator at [contact].

OnCore is designed with the capability for study setup, activation, tracking, reporting, data monitoring and review, and eligibility verification. This study will utilize electronic Case Report Form completion in the OnCore database. A calendar of events and required forms are available in OnCore.

REDCap will be utilized to collect quality of life data directly from the patients, using the following weblink: <http://j.mp/2eLzfjE>. This link will be accessed on a password protected tablet computer by the clinical trials nurse on the day when quality of life data is to be collected. The clinical trials nurse will enter the patient's study ID into the survey instrument and then the patient will complete the rest of the electronic form and submit it. REDCap is a secure, web-based application for building and managing online surveys and databases. REDCap is an NIH-sponsored application and follows HIPAA guidelines. The WVCTSI instance of REDCap is housed at the Ruby Office Complex (ROC) which was built in 2008 and designed by IBM. It is a fully redundant building with generator backup that is manned and monitored 24/7 with onsite staff, closed-circuit camera, automated reporting systems. It's secure by magnetic locks and only accessible via card access. Systems are secured through multiple layers of security including encryption, firewalls, reverse proxy and tested regularly for vulnerabilities. The OnCore Administrator [contact] will be able to access the data reported from all patients at the time of analysis.

12.1.1. Method

Data will be submitted on a real-time basis, within 2 weeks of the protocol-related visit via OnCore electronic case report forms.

12.1.2. Responsibility for Data Submission

It is the responsibility of the PI(s) at the site to ensure that all investigators understand the procedures for data submission and that protocol specified data are submitted accurately and in a timely manner via the electronic data capture system, OnCore.

Metrics for timeliness will be followed and assessed on a quarterly basis. For the purpose of Institutional Performance Monitoring, data will be considered delinquent if it is greater than 4 weeks past due.

12.2. Regulatory Considerations

The study will be conducted in compliance with ICH guidelines and with all applicable federal (including 21 CFR parts 56 & 50), state or local laws.

12.2.1. Written Informed Consent

Provision of written informed consent must be obtained prior to any study-related procedures. The Principal Investigator will ensure that the subject is given full and adequate oral and written information about the nature, purpose, possible risks and benefits of the study as well as the subject's financial responsibility. Subjects must also be notified that they are free to discontinue from the study at any time. The subject should be given the opportunity to ask questions and be allowed time to consider the information provided.

The original, signed written Informed Consent Form must be kept with the Research Chart in conformance with the institution's standard operating procedures. A copy of the signed written Informed Consent Form must be given to the subject. Additionally, documentation of the consenting process should be noted in the medical record.

12.2.2. Subject Data Protection

In accordance with the Health Information Portability and Accountability Act (HIPAA), a subject must sign an authorization to release medical information to the sponsor and/or allow the sponsor, a regulatory authority, or Institutional Review Board access to subject's medical information that includes all hospital records relevant to the study, including subjects' medical history.

12.2.3. Retention of records

The Principal Investigator supervises the retention of all documentation of adverse events, records of study drug receipt and dispensation, and all IRB correspondence for as long as needed to comply with national and international regulations. No records will be destroyed until the Principal Investigator confirms destruction is permitted.

12.2.4. Audits and inspections

Authorized representatives of the sponsor, a regulatory authority, an Independent Ethics Committee (IEC) or an Institutional Review Board (IRB) may visit the site to perform audits or inspections, including source data verification. The purpose of an audit or inspection is to systematically and independently examine all study-related activities and documents to determine whether these activities were conducted, and data were recorded, analysed, and accurately reported according to the protocol, Good Clinical Practice (GCP), guidelines of the International Conference on Harmonization (ICH), and any applicable regulatory requirements.

12.2.5. Data Safety and Monitoring Plan

This protocol will adhere to the policies of the WVU Mary Babb Randolph Cancer Center Data and Safety Monitoring Plan.

13. STATISTICAL CONSIDERATIONS

13.1. Study Design/Endpoints

The primary endpoint is the best overall response rate (complete and partial) after the initial course of radiation therapy with concurrent immune therapy. The secondary objectives include determination of the progression-free and overall survival at 1 year, toxicity, and quality of life. Correlative objectives include an assessment of levels of circulating CD4+, CD8+ and Treg T-cell subsets, iNOS+ macrophages, and the chemokines CCL2, CXCL9, CXCL10, and CXCL11 in relation to clinical response.

13.2. Sample Size/Accrual Rate

The primary analysis will be for patients enrolled at time-points (A) and (B) above, whereas patients enrolled at time-point (C) will be included in observational analysis only (see section 3.1). The primary endpoint of this study is the overall response rate (complete + partial response) and the efficacy will be assessed using the Simon's two-stage Minmax design. A sample size of 33 patients is chosen to differentiate between the response rate of 20% and 40% with 80% power at a significance level of 0.05. In particular, 18 patients will be enrolled at the first stage. If 15 or more of the first 18 patients have disease progression prior to any response, the trial will be terminated; otherwise an additional 15 patients will be treated for a total of 33 patients. In the final data analysis, if 10 or fewer patients respond among 33 patients, the treatment will be concluded ineffective. The probability of early termination due to futility is 0.72.

For correlative study between biomarkers and response, this sample size will have at least 80% power to detect a 50% change/difference on biomarker data between response and non-response groups using a two-sided two-sample t-test at 0.05 significance level, assuming that the response rate is 35% or higher and the coefficient of variation (CV) of biomarkers is 0.45.

Approximately 100 patients with metastatic NSCLC are diagnosed and treated each year at our institution, many of whom will be candidates for immune checkpoint therapy. As such, we expect to accrue 3 patients per month to this trial for an estimated accrual period of one year. The full estimated duration of the study is two years.

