11. MEASUREMENT OF EFFECT

11.1. Antitumor Effect

11.1.1. Imaging Modalities

At baseline and follow-up, systemic response (for unirradiated lesions) and local response (for irradiated lesions) will be assessed using FDG-PET/CT (preferred) or CT scan of the chest/abdomen/pelvis. Ideally IV contrast and CT slice thickness $\leq 5\text{mm}$ will be used for either type of study. Images will be acquired according to the standard of care schedule used for patients receiving immune checkpoint therapy, at intervals of 4 months or less after initiation of immune therapy. In the event of an imaging study showing disease progression, a confirmatory scan is recommended at least 4 weeks later to confirm progression. The same method of assessment and technique should be used to characterize each index lesion at baseline and during follow-up. All measurements should be recorded in metric notation and specified to the nearest millimeter. All baseline evaluations should be performed as closely as possible to the beginning of treatment and never more than 4 weeks before the beginning of the treatment. Imaging-based evaluation is preferred to evaluation by clinical examination unless the lesion(s) being followed cannot be imaged but are assessable by clinical exam.

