11.1.2. Definitions

Evaluable for objective response: Only those patients who have received at least one course of radiation therapy, and have had their disease re-evaluated by imaging at least 4 weeks after initiation of therapy will be considered evaluable for response. These patients will have their response classified according to the definitions stated below.

Immune-Related Response Criteria (irRC)⁴³⁻⁴⁴: Novel criteria for the evaluation of antitumor responses with immunotherapeutic agents, as described in Wolchok *et al.* The patterns of response to immune therapy agents differ from those of cytotoxic therapy in several ways: There may be a transient worsening of disease before stabilization or regression, responses can take months to become apparent and may continue long after completion of the initial therapy, and prolonged periods of stable disease are common. For the purposes of this study, irRC will be used for evaluation of all **non-irradiated** index lesions and the unit of measure will be the sum of the products of the two largest perpendicular diameters (SPD) for all index lesions.

Response Evaluation Criteria in Solid Tumors (RECIST) Version 1.1⁴⁵: Method for the evaluation of antitumor responses to cytotoxic agents, as described by Eisenhauer *et al.* For the purposes of this study, RECIST 1.1 criteria will be used only for the evaluation of **irradiated** lesions and the unit of measure will be the single largest diameter.

Measurable lesions on initial imaging: Measurable malignant lesions on *initial* imaging are defined as those that can be accurately measured in at least one dimension as $\geq 10\text{ mm}$ ($\geq 1.0\text{ cm}$) with CT or PET/CT scan. Lymph nodes will be considered malignant (and thus measurable lesions) if their short axis is $\geq 15\text{ mm}$ ($\geq 1.5\text{ cm}$) by CT scan. All other lesions will be considered non-measurable disease. Bone lesions without a soft

tissue component, leptomeningeal disease, ascites, pleural/pericardial effusions, lymphangitis cutis/pneumonitis, inflammatory breast disease, and abdominal masses (not followed by CT or MRI), are considered non-measurable. Simple cysts are by definition non-malignant and non-measurable, but cystic metastases can be considered as measurable lesions, if they meet the size cutoff of measurability described above. Tumor lesions that are situated in a previously irradiated areas are not considered measurable.

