11.2. Response Criteria

The irRC criteria for assessing systemic disease response (including only non-irradiated lesions) can be seen in the following table:

New, measurable lesions (ie, $\geq 5 \times 5$ mm)	Incorporated into tumor burden
New, non-measurable lesions (ie, $< 5 \times 5$ mm)	Do not define progression (but preclude irCR)
Non-index lesions	Contribute to defining irCR (complete disappearance required)
irCR	Disappearance of all lesions in two consecutive observations at least 4 weeks apart
irPR	$\geq 50\%$ decrease in tumor burden compared with baseline in two observations at least 4 weeks apart
irSD	Neither sufficient decrease in tumor burden to qualify as irPR

	nor sufficient increase in tumor burden to qualify as irPD.
irPD	$\geq 25\%$ increase in tumor burden compared with nadir (at any single time point) in two consecutive observations at least 4 weeks apart.

Examples of irRC overall response³⁷:

Measurable response Index and new, measurable lesions (tumor burden),* %	Nonmeasurable response		Overall response Using irRC
	Non-index lesions	New, nonmeasurable lesions	
↓100	Absent	Absent	irCR [†]
↓100	Stable	Any	irPR [†]
↓100	Unequivocal progression	Any	irPR [†]
↓≥50	Absent/Stable	Any	irPR [†]
↓≥50	Unequivocal progression	Any	irPR [†]
↓<50 to <25↓	Absent/Stable	Any	irSD
↓<50 to <25↓	Unequivocal progression	Any	irSD
≥25↓	Any	Any	irPD [†]

*Decreases assessed relative to baseline, including measurable lesions only (>5 x 5 mm).
†Assuming response (irCR) and progression (irPD) are confirmed by a second, consecutive assessment at least 4 wk apart.

RECIST version 1.1 will be used to assess the local response of irradiated lesions only, taking as reference the baseline largest diameter:

Complete Response (CR)	Disappearance of the irradiated lesion
Partial Response (PR)	$\geq 30\%$ decrease in the single largest diameter of the irradiated lesion
Stable Disease (SD)	Neither sufficient decrease in diameter to qualify as PR nor sufficient increase in diameter to qualify as PD
Progressive Disease (PD)	$\geq 20\%$ increase in the single largest diameter of the irradiated lesion. In addition to the relative increase of 20%, the sum must also demonstrate an absolute increase of at least 5 mm (0.5 cm).

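### The early-termination probability of 0.72 does not belong to the written stage-1 rule, which stops with probability at most 0.50 at a 20% response rate

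*Combined protocol and SAP*

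**What the plan says.** Section 13.2 names Simon's two-stage minimax design for the overall response rate: "A sample size of 33 patients is chosen to differentiate between the response rate of 20% and 40% with 80% power". Alpha is set to 0.05. Eighteen patients enter stage 1, and 15 more follow if the trial is not stopped. The stage-1 rule is: "If 15 or more of the first 18 patients have disease progression prior to any response, the trial will be terminated". The final rule is: "if 10 or fewer patients respond among 33 patients, the treatment will be concluded ineffective". The section then states: "The probability of early termination due to futility is 0.72". It does not say at which response rate that probability applies or when the stage-1 look takes place. No other section restates the stage-1 boundary.

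Three points elsewhere bear on the rule. Stable disease is a response category of its own (Section 11.2), so a non-responder need not have progressed. Best response is recorded only up to progression, and Section 11.2.1 adds that the "best response assignment will depend on the achievement of both measurement and confirmation criteria". Section 11.1.2 warns that "responses can take months to become apparent".

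**The concern.** A Simon design is fixed by four numbers: the two sample sizes and the two response cut-offs. Section 13.2 gives both sample sizes and the final cut-off directly, but writes the stage-1 cut-off as a count of progressions. Turned into responders, that count is one step away from the boundary that produces 0.72.

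A review committee reading 0.72 would expect an ineffective treatment to stop after 18 patients about 7 times in 10. If the rule as written does so at most 5 times in 10, the plan overstates its futility protection. The conflict is also practical. With 4 responders and 14 progressions among the first 18, the named design stops and the written rule continues.

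**Working it through.** **Inputs, all from Section 13.2.** p0 = 0.20, p1 = 0.40, n1 = 18, N = 33; effective only if at least 11 of 33 respond; stop at stage 1 if at least 15 of 18 progress before responding; stated early-termination probability 0.72. The 0.05 level is taken as one-sided, as is usual for this design; this does not affect the early-termination probability.

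**Step 1. Reproduce the stated figure.** An exact search over two-stage designs with p0 = 0.20, p1 = 0.40, alpha ≤ 0.05 and power ≥ 0.80 gives a minimum N of 33. Among designs of that size, the smallest expected N under p0 has n1 = 18, stage-1 boundary r1 = 4 and final boundary r = 10. For X ~ Bin(18, 0.20):

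| x | 0 | 1 | 2 | 3 | 4 |
|---|---|---|---|---|---|
| P(X = x) | 0.0180 | 0.0811 | 0.1723 | 0.2297 | 0.2153 |

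P(X ≤ 4) = 0.7164, the plan's 0.72. Every stated element matches this design except the stage-1 rule. Four or fewer responders of 18 means 18 − 4 = 14 or more non-responders.

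**Step 2. The written rule.** If 15 or more of 18 progress before any response, at most 18 − 15 = 3 can be responders. Patients who progress first are a subset of the non-responders, so

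P(stop | 0.20) ≤ P(X ≤ 3 | 18, 0.20) = 0.7164 − 0.2153 = 0.5010 (unrounded terms),

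with equality only if every non-responder has progressed by the look.

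**Step 3. Operating characteristics.** Expected N = 18 + 15 × (1 − P(stop | 0.20)). Alpha and power are the exact probabilities, at 0.20 and 0.40, of continuing past stage 1 and reaching at least 11 responders of 33.

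| | P(stop), 20% | Expected N, 20% | P(stop), 40% | Alpha | Power |
|---|---|---|---|---|---|
| Named design (≤ 4 of 18 respond) | 0.716 | 22.25 | 0.094 | 0.0458 | 0.801 |
| Written rule, all non-responders progressed | 0.501 | 25.48 | 0.033 | 0.0497 | 0.825 |

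The difference in expected N is 25.48 − 22.25 = 3.23 patients. The two rules part company at exactly 4 responders: probability 0.215 at a 20% rate and 0.061 at 40%.

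**Step 4. Stable patients at the look.** The documents give no stable share, so these shares of all patients are assumptions. Stage 1 is treated as trinomial (response, stable, progression), and stopping requires at least 15 progressions.

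| Assumed stable share | P(stop), 20% | Expected N, 20% | Alpha | Power |
|---|---|---|---|---|
| 0% | 0.501 | 25.48 | 0.0497 | 0.825 |
| 2.5% | 0.398 | 27.04 | 0.0501 | 0.828 |
| 5% | 0.306 | 28.41 | 0.0504 | 0.829 |
| 10% | 0.165 | 30.53 | 0.0506 | 0.831 |
| 20% | 0.033 | 32.51 | 0.0508 | 0.831 |

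**Step 5. Could 0.72 refer to another response rate?** Under the written cut-off with no stable patients, P(X ≤ 3 | 18, p) = 0.72 at p of about 0.15. The stated null is 20%, and Section 2.2 cites 19–25% for checkpoint inhibitors alone, so the plan gives no basis for 15%.

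**The case against.** The strongest case on the other side accepts the arithmetic and argues about weight and remedy.

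- **The final decision is sound.** At the ceiling, alpha is 0.0497 and power 0.825, both within the plan's targets. The highest alpha, 0.0508, is the value with no interim stop at all. The immune therapy is standard of care and the radiation doses are described as within standard practice, so a late futility stop has limited consequences. This stands, and it is why the point calls for a correction and does not condemn the design.
- **The 3.2 extra patients depend on holding enrolment at 18.** Section 13.2 makes the further 15 conditional on the stage-1 result, so expected N is the ordinary two-stage quantity. But the section states no accrual hold and no look date, and without a hold either rule could save few patients or none. This qualification stands.
- **Counting progressions may be deliberate,** because immune responses can be late. That is reasonable and is not treated as an error here. It does not rescue 0.72: the probability of the progression rule is still capped at 0.501.
- **The slip may be a single digit.** Changing 15 to 14 and keeping progression as the event would give at most 0.716. With assumed stable shares of 5% and 10%, early termination is 0.519 and 0.333, alpha 0.0484 and 0.0497, and power 0.820 and 0.828; at 20% stable, alpha is 0.0507. This is a workable further route, but it too would have to present 0.72 as a maximum.

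**Conclusion.** The concern holds. The 0.72 and the minimax label belong to a stage-1 boundary of 4 or fewer responders of 18. The written cut-off of 15 progressions gives at most 0.501 at a 20% response rate. That ceiling needs no assumption about stable disease, only that a patient who progresses first is not later counted as a responder, which is how Section 11.2.1 defines best response. The cost is weaker futility stopping: 0.215 less probability of stopping and 3.2 more expected patients at a 20% rate, given that enrolment waits for the look, and more if some patients are stable. The final test at 10 of 33 is barely affected. It should be fixed, as a short correction to Section 13.2.

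**What to change.** Amend Section 13.2 in one of two ways. Both leave 18 and 33 unchanged.

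**(a) State the boundary in responders.** For example: *If 4 or fewer of the first 18 patients have a response (irCR or irPR), the trial will be terminated; at a true response rate of 20% the probability of this is 0.72.* Apply it once each of the 18 has either responded or can be classed as a non-responder.

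- *Power.* It is 0.80, against about 0.83 under the written rule, and only if classification is complete at the look. If the look were taken early and pending responders counted as failures, power would fall to 0.781, 0.753 or 0.672 when 5%, 10% or 20% of eventual responders are unconfirmed (assumed shares).
- *Time.* Scans are due "at intervals of 4 months or less after initiation of immune therapy", and a partial response requires a "decrease in tumor burden compared with baseline in two observations at least 4 weeks apart". A response first seen at a 4-month scan is therefore confirmed about 5 months after the 18th patient starts; later responses take longer. At the planned 3 patients per month, 5 × 3 = 15 patients of accrual time if enrolment is held.

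**(b) Keep the progression rule and correct its description.** Replace 0.72 with at most 0.50 at a 20% response rate, give power as about 0.83 and alpha as about 0.050 (0.0497 to 0.0508 for assumed stable shares of 0 to 20%), and say that the stage-1 boundary is not the minimax one. Nothing changes in operation, and the trial does not stop on pending responders. The document must then admit weaker futility stopping and an alpha that may slightly exceed 0.05.
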